**Table 7 Guideline for treatment of patients experiencing adverse events**

Recommended dose modifications for pasireotide/ placebo	
Worst toxicity CTCAE Grade* (value)	Recommended dose modification any time during a cycle of therapy
No toxicity	Maintain dose level
Hematologic	
Neutropenia (ANC)	
Grade 1 (ANC < LLN - 1500/mm  )	Maintain dose level
Grade 2 (ANC < 1500 - 1000/mm  )	Maintain dose level
Grade 3 (ANC < 1000 - 500/mm  )	Omit dose until resolved to ≤ Grade 2, then ↓ 1 dose level 
 
• If resolved ≤ 7 days, then maintain dose level
 
• If resolved > 7 days, then ↓ 1 dose level
 

Grade 4 (ANC < 500/mm  )	Omit dose until resolved to ≤ Grade 2, then ↓ 1 dose level 
 
• If resolved ≤ 7 days, then maintain dose level
 
• If resolved > 7 days, then ↓ 1 dose level
 

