**Hepatic See also section 7.5.4.1****Bilirubin**

Grade 1 (< 2 x baseline value)	Maintain dose level
Grade 2 (2-3 x baseline value)	Omit dose until resolved to ≤ Grade 1, then 
 
• If resolved ≤ 7 days, then maintain dose level
 
• If resolved > 7 days, then ↓ 1 dose level
 

Grade 3 (> 3.0 - 10.0 x ULN)	Omit dose until resolved to ≤ Grade 1, then 
 
• If resolved ≤ 7 days, then maintain dose level
 
• If resolved > 7 days, then ↓ 1 dose level
 

Grade 4 (> 10.0 x ULN)	Omit dose and discontinue patient from study treatment

NOTE: If grade 3 or 4 hyperbilirubinemia is due to the indirect (unconjugated) component only, and hemolysis as the etiology has been ruled out as per institutional guidelines (e.g. review of peripheral blood smear and haptoglobin determination), then ↓ 1 dose level and continue treatment at the discretion of the investigator

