## 6.8 Study drug discontinuation

Study drug must be discontinued and the subject withdrawn from the trial if the investigator determines that continuing would result in significant safety risk for that subject. The following circumstances require study drug discontinuation:

Pregnancy

The occurrence of an adverse event or of a clinically significant laboratory change or abnormality that, in the judgment of the investigator, warrants discontinuation of treatment.

Subjects who have fasting plasma glucose > 240 mg/dL confirmed by repeat measurement

Any CTC grade 3 or higher abnormalities in hematology or chemistry parameters judged clinically significant by the Investigator

Any confirmed QTcF > 500 ms or confirmed increase of QTcF > 60 ms from baseline

ALT or AST > 3x ULN and Total Bilirubin  $\geq$  2 x ULN and ALP > 2 x ULN

ALT or AST > 5x ULN and  $\leq$  8 x ULN persistent for more than 2 weeks

ALT or AST > 8 x ULN

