#### **7.5.4.1 Abnormal liver function management:**

Perform within 72 hours of awareness of abnormal LFTs:

Perform liver-directed medical history and physical examination (i.e. assess occupational hazards, concomitant medications including OTC meds, intercurrent illness, etc)

Liver chemistry tests: ALT, AST, total bilirubin, (fractionate to direct/indirect bilirubin if total bilirubin is > 2.0x ULN), Alb, PT (INR), ALP, and GGT

Perform hepatitis screen: anti-HAV, IgM (to confirm acute hepatitis A), HbsAg, Anti-HBc, anti-HCV (if positive PCR viral load should be assessed), Anti-HEV, ANA antibodies, anti-smooth muscle anti-bodies, CMV, EBV

Perform abdominal ultrasound (liver and biliary tree)

Liver chemistry tests should be monitored every 3-4 days for LAR studies until resolution or return to baseline status.

For ALT or AST > 5x ULN and ≤ 8x ULN:

- Study medication should be temporarily interrupted and liver chemistry tests monitored **every 3-4 days** until resolution or return to baseline
- If resolution or return to baseline does not occur after 2 weeks, the patient should be discontinued.
- If ALT or AST returns to less than 5x ULN, study drug can be resumed and patient can continue study per protocol
- If ALT or AST rises above 5x ULN anytime after study drug is resumed, then study drug should be discontinued immediately.

Resolution return to baseline does not occur after two weeks the patient should be discontinued

If ALT or AST rises about 5X ULN anytime after study drugs resumed and study drug to be discontinued immediately

Study medication should be discontinued immediately if any of the discontinuation criteria below are met: (see appendix 4)

ALT or AST > 3x ULN and Total Bilirubin ≥ 2x ULN and ALP < 2x ULN

ALT or AST > 5x ULN and ≤ 8x ULN persistent for more than 2 weeks

ALT or AST > 8x ULN

Re-challenge of study medication is prohibited once discontinuation criteria are met.

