## 12.4 Appendix 4 SOM230 LFT Management Algorithm (s.c. and LAR Studies)

### Revised SOM230 Abnormal liver function discontinuation criteria:

Hepatic-related discontinuation criteria for all ongoing studies
Study medication should be discontinued immediately if any of the discontinuation criteria below are met:

 
ALT or AST > 3x ULN and Total Bilirubin ≥ 2x ULN and ALP < 2x ULN
 
ALT or AST > 5x ULN and ≤ 8x ULN persistent for more than 2 weeks
 
ALT or AST > 8x ULN
 

Re-challenge of study medication is prohibited once discontinuation criteria are met.

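### Section 6.8 reverses the ALP limb of the combined liver stopping criterion (above 2x ULN, against below 2x ULN in 7.5.4.1 and Appendix 4); the sections need reconciling, with an explicit decision for patients at ALP 2x ULN or more

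*Combined protocol and SAP*

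**What the plan says.** The combined hepatic criterion appears three times in the combined protocol and SAP.

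- **Section 6.8 (Study drug discontinuation)** introduces its list with "The following circumstances require study drug discontinuation". The combined line takes ALT or AST above 3x ULN, with total bilirubin at or above "2 x ULN and ALP > 2 x ULN". Section 6.10 (Overall Study Stopping Rules) sends the reader to 6.8 for stopping criteria based on chemistry values.
- **Section 7.5.4.1 (Abnormal liver function management)** lists, for immediate discontinuation, "ALT or AST > 3x ULN and Total Bilirubin ≥ 2x ULN and ALP < 2x ULN". It adds: "Re-challenge of study medication is prohibited once discontinuation criteria are met".
- **Appendix 4 (section 12.4)** repeats the 7.5.4.1 version under a heading that calls the criteria revised, introduced by "Study medication should be discontinued immediately if any of the discontinuation criteria below are met". It repeats the re-challenge ban.

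The other two hepatic lines are the same in all three places: ALT or AST above 5x and up to 8x ULN for more than 2 weeks, and ALT or AST above 8x ULN.

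Table 7 in section 6.6 grades bilirubin and AST/ALT in separate rows and has no combined row. It is headed "Recommended dose modifications for pasireotide/ placebo", and its liver block opens with "Hepatic See also section 7.5.4.1". A note there allows treatment to continue one dose level lower, at the investigator's discretion, when a Grade 3 or 4 bilirubin rise is indirect only and hemolysis has been ruled out.

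**The concern.** Only the direction of the ALP inequality differs, but it decides which patients the criterion selects. Section 6.8 is written as the required stop list and 6.10 cites it for chemistry values, so site staff may well go there first. Neither 6.8 nor 6.10 points to 7.5.4.1. A reader who stops at 6.8 sees no numeric line for raised transaminases and bilirubin with ALP below 2x ULN. What remains there is judgment, for example "Any CTC grade 3 or higher abnormalities in hematology or chemistry parameters judged clinically significant by the Investigator". A reader who uses only 7.5.4.1 or Appendix 4 sees no combined line for the same picture with ALP above 2x ULN.

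At stake is whether the same laboratory result leads to the same action whichever section is opened. For the lower-ALP patient it also matters whether the re-challenge ban is seen.

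**Working it through.** This is a comparison of texts. No sample size, power or alpha figure is involved, and the plan states no figure to reproduce. All values below are multiples of ULN.

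**1. The ALP limb.** The 6.8 test is ALP > 2. The 7.5.4.1 and Appendix 4 test is ALP < 2. No value meets both, and ALP = 2.0 meets neither. Taken together they cover every other value.

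**2. Two example patients**, both with ALT 4 and bilirubin 2.5.

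| Criterion | A: ALP 1.2 | B: ALP 2.5 |
|---|---|---|
| 6.8 combined line (ALT > 3, bilirubin ≥ 2, ALP > 2) | not met: 1.2 is not > 2 | met |
| 7.5.4.1 / Appendix 4 combined line (ALT > 3, bilirubin ≥ 2, ALP < 2) | met: stop at once, no re-challenge | not met: 2.5 is not < 2 |
| ALT > 5 to 8 for more than 2 weeks (all three places) | not met | not met |
| ALT > 8 (all three places) | not met | not met |

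Patient B's ALP equals the entry ceiling: section 5.2.1 admits alkaline phosphatase up to 2.5x ULN. A patient whose ALP stays above 2x ULN from entry cannot meet the 7.5.4.1 combined line. For that patient the 6.8 line is the only combined numeric stop in the protocol.

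**3. Extent by transaminase band**, with bilirubin ≥ 2 and ALP < 2.

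| ALT or AST | 6.8 numeric lines | 7.5.4.1 |
|---|---|---|
| > 3 to 5 | none | immediate stop |
| > 5 to 8 | stop after more than 2 weeks | immediate stop |
| > 8 | stop | immediate stop |

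In the middle band, Table 7 and 7.5.4.1 both already call for interruption, with liver tests every 3-4 days. The practical difference is therefore mainly in the > 3 to 5 band.

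**4. Table 7 for patient A.** The AST/ALT row (Grade 2, > 2.5 to 5.0) says to maintain the dose. The bilirubin row depends on baseline bilirubin b, which may be up to 1.5 at entry. The three values of b are assumptions.

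- b = 1.5: 2b = 3.0, and 2.5 < 3.0, so maintain.
- b = 1.0: 2b = 2.0 and 3b = 3.0, so 2.5 falls in Grade 2: omit, then resume.
- b = 0.8: 3b = 2.4 < 2.5, and Grade 3 begins above 3.0, so no row matches.

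For bilirubin ≥ 2, the maintain row requires 2b > 2, that is b > 1.0. At b = 1.0 the first action (omit) agrees with 7.5.4.1, and only the later resumption conflicts.

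**The case against.** A reader might infer that the protocol loses a mandatory liver stop, leaving patient A to the investigator's judgment. The documents do not support that. Section 7.5.4.1 is itself an operative rule that requires immediate discontinuation. It is the section written for abnormal liver tests, and it also contains the 72-hour work-up. Appendix 4 repeats the rule, and section 1.5.2.1 directs readers to that appendix. Nothing makes 6.8 exhaustive or gives it priority, and nothing in it authorizes continuing. Read cumulatively, the sections stop every patient with ALT or AST above 3x and bilirubin at least 2x ULN, except at ALP exactly 2x ULN. The protocol as a whole is therefore stricter than any one section.

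A second tempting reading is that Table 7 instructs sites to resume a drug that must not be re-challenged. Its rows are recommendations for single analytes and its liver heading points to 7.5.4.1. A specific mandatory criterion would naturally control. The table does not say so, however, and its indirect-bilirubin note makes no exception for the combined criterion.

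A third point concerns the remedy. Simply reversing the sign in 6.8 would remove the only combined numeric stop for ALP above 2x ULN, a group that the entry criteria admit. That objection stands, and the fix has to deal with it.

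What survives is the contradiction itself. It concerns a decision threshold in the list that requires discontinuation, and which action a reader finds depends on the section consulted.

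**Conclusion.** The inconsistency is real and should be corrected. Section 6.8 and the pair 7.5.4.1 and Appendix 4 select disjoint groups on ALP. Someone using 6.8 alone would find no numeric stop for ALT 4x, bilirubin 2.5x and ALP 1.2x ULN; someone using 7.5.4.1 or Appendix 4 alone would find no combined stop at ALP 2.5x ULN. Across the whole protocol, only ALP of exactly 2x ULN escapes both combined lines.

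That 6.8 carries the unintended sign is an inference. It rests on two sections agreeing against one, and on Appendix 4 being headed as revised criteria; the documents do not say which version is right. The need to reconcile them does not depend on the answer. The documents give no frequency for this event, so the number of patients affected cannot be stated. The silence of Table 7 on precedence is a lesser matter of clarity.

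**What to change.** 1. In 6.8, state the combined criterion as ALT or AST above 3x ULN, total bilirubin at or above 2x ULN and ALP below 2x ULN, matching 7.5.4.1 and Appendix 4.
2. Have the sponsor decide explicitly whether to keep a separate stop for the same transaminase and bilirubin levels with ALP at or above 2x ULN. If it is kept, give it its own line in 6.8, 7.5.4.1 and Appendix 4, and say whether the re-challenge ban applies. Using at or above, in place of above, also closes the gap at exactly 2x ULN. If it is dropped, record the reason, given the entry limit of 2.5x ULN.
3. As a secondary clarification, state under Table 7's hepatic heading that the discontinuation criteria and re-challenge ban in 7.5.4.1 and Appendix 4 override the single-analyte rows and the indirect-bilirubin note.

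The cost is one corrected line, one sponsor decision (with an added line if the stop is kept) and one sentence. No new tests are needed: total bilirubin, AST, ALT and ALP are already in the scheduled metabolic panel (Table 8, footnote 4).

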## 6.9 Premature patient withdrawal

Patients may voluntarily withdraw from the study or be dropped from it at the discretion of the investigator at any time. These patients will be asked to complete an Early Termination Visit. Patients may be withdrawn from the study if any of the following occur:

Lack of efficacy

Uncontrolled diabetes mellitus (DM)

Pregnancy

Adverse event(s)

Abnormal laboratory value(s)

Abnormal test procedure result(s)

Protocol violation

Subject withdrew consent

Lost to follow-up

Administrative problems

Death

New therapy for disease being investigated

Disease progression

## 6.10 Overall Study Stopping Rules

Stopping criteria for hyperglycemia and other side effects, e.g. related to changes in hematology, chemistry, or cardiac test values are **listed in section 6.8**. Pasireotide has already demonstrated acceptable tolerability and efficacy in several completed or ongoing clinical trials (**page 38 Investigator Brochure**) and the LAR formulation is being examined in a phase 3 study for treatment of Acromegaly NCT00600886; Novartis data on file, and for Cushing disease (sc formulation; CSOM230B2305] recently reported (Colao, Petersenn et al. 2012). In the latter study hyperglycemia-related adverse events occurred in 73% of patients necessitating 6% discontinuing study treatment Plasma glucose levels increased 10% from baseline compared with a 2% increase in placebo ( $P<0.02$ ) after commencing octreotide treatment and no patient developed diabetes in our prior somatostatin analog study using OctLAR.

Gastrointestinal problems are the most commonly reported AEs associated with the use of SOM230, (predominantly mild diarrhea grade 1 or 2, and nausea requiring no treatment or study discontinuation). In our prior somatostatin analog study in PKD, only 1/42 individuals discontinued that study after one year (due to steatorrhea) and none discontinued because they developed diabetes. Based on our prior experience and others' studies of tolerability and side effects associated with OctLAR (and also with lanreotide in PKD and PLD), we do not anticipate there will be patient discontinuation >15%, since both drugs have a similar tolerability profile (**Investigator brochure section 6.2**). Hence, we do not anticipate we will need to stop this study in this patient population due to lack of study power. If there is no efficacy found after the first year analysis is complete then we will terminate the open label extension. We will be monitoring each patient closely (**table 8**) for expected and unexpected drug side effects. If there are any

serious suspected adverse reactions (>1) that were unexpected these would be evaluated by the sponsor-investigator and the risk/benefit of study continuation would be analyzed. Novartis also reserves the right to stop the study (**section 13.1.3**).

- Colao, A., S. Petersenn, et al. (2012). "A 12-Month Phase 3 Study of Pasireotide in Cushing's Disease." New England Journal of Medicine **366**(10): 914-924.

## **6.11 End of treatment**

Treatment duration will be completed per the protocol

## **7 Visit schedule and assessments**

Table 8 lists all of the assessments and indicates the visits at which they are to be performed with an "X". All data obtained from these assessments must be supported in the patient's source documentation. In year 2, safety assessments for patient's crossing over from placebo to SOM 230 will be required. These will be per the same schedule after the first SOM230 injection as was performed in year 1 for all patients enrolled.

**Table 8 Visit/Study Procedure Schedule**

Test / Procedure	S	R	Days after 1 st injection					Months after initial visit											Mos. after end					
			22/2	29	50	57	85	6	9	12 	15	18	21	24	27	30	33	36 / Early Term	1	3				
Consent	X																							
History/physical	X							X		X		X		X		X		X		X				
Height,  Weight	X							X		X				X		X		X		X				
ECG 	X	X	X		X		X	X	X	X	X	X	X	X	X	X	X	X	X	X	X	X	X	
Heme Group 	X							X	X	X	X	X	X	X	X	X	X	X	X	X	X	X	X	
PT APTT	X							X		X					X							X		
Metabolic panel  eGfr 	X		X	X	X	X	X	X	X	X	X				X							X		
Hemoglobin A1C 	X						X	X	X	X	X	X	X	X	X	X	X	X	X	X	X	X	X	X
Thyroid cascade 	X							X		X	X	X			X			X			X			
MRI (CT) Scan	X									X												X		
Genotyping	X																							
Cyclosporin level 	X				X			X	X	X	X	X			X							X		
Microalbumin	X									X					X							X		
Fasting glucose 	X	X	X		X		X	X	X	X	X	X	X	X	X	X	X	X	X	X	X	X	X	X
Pregnancy Test 	X									X														
QOL SF-36v2TM	X							X		X				X			X		X		X			
SOM230/Placebo 		X	X		X	X	X	X	X	X	X	X	X	X	X	X	X	X	X	X	X	X	X	X
Concomitant meds	X	→	X	X	X	X	X	X	X	X	X	X	X	X	X	X	X	X	X	X	X	X	X	X
Gallstone (6 mo) 								X					X		X			X						
PK Bloods	X			X			X	X		X														

S= Screening

R = Randomization

 Height required only at pre-study 12 lead ECG & interpretation at screening and ½ hour after first injection. Repeat ECG on 21st day after injection for the first 3 months then every third month. All ECGs are faxed to the Mayo Clinic ECG Core lab. Includes WBC with differential Comprehensive fasting metabolic panel includes: albumin, total bilirubin, calcium, CO2, (bicarbonate) chloride, creatinine, BUN, potassium, total protein, sodium, AST, ALT, ALP,, and glucose. Liver function tests are assessed at baseline (if baseline LFTs are **done within 7 days of day 1 of treatment** they do not have to be repeated on day 1), day 22 after first injection, day 29, day 50, 57 and 85. After day 85 and the 4th LAR Injection, monitoring should follow the existing protocol schedule. Day 22 & 50 LFTs must be available & assessed prior to dosing on days 29 (2nd injection) and 57 (3rd injection). Only in patients with associated PKD. Hemoglobin A1C is done at baseline and 3 monthly Thyroid function is also acceptable if checked within 30 days of the screening visit Bi-weekly cyclosporin levels will be monitored for the first month in enrolled patients who are on this medication (mail in test) Plasma glucose is required 6 hours after first injection. Monitor FPG or finger stick at baseline and at 21st day of treatment for first 3 months. Monitor FPG or finger stick monthly (or as clinically appropriate), thereafter.

-  Women of childbearing potential only (urine pregnancy test). If CT scan is needed, a negative pregnancy result will need to be obtained prior to performing the CT. For women of child bearing potential who will be having an MRI – a pregnancy test is not required at month 12.
-  SOM230/placebo IM injections will be given every 28 days, +/- 2 days.
-  No gallstone assessment is needed on visits where MRI is performed, as gallstones will be detected on MRI if present.
-  In year 2, safety assessments for patients crossing over from placebo to SOM 230 will be required. These will be per the same schedule after the first SOM230 injection as was performed in year 1 for all patients enrolled.

At a minimum the following safety evaluations (Table 9) are to be included in all protocols.

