#### **1.5.1.1.1 Clinical pharmacokinetics**

Pasireotide SQ and LAR have been studied in healthy volunteers, patients with acromegaly, Cushing's disease and carcinoid syndrome. Following a single IM injection of 40 mg or 60 mg in healthy volunteers [CSOM230C2101], pasireotide LAR demonstrated a controlled release type of concentration-versus-time profile, with an initial spike phase on day 1 followed by a slow-release process for up to 42 days. The Cmax of the extended release phase was observed approximately on day 20 for both dose levels. Pasireotide LAR was also investigated in patients with acromegaly and carcinoid tumors [CSOM230C2110]. Following monthly (q28 days) IM injections of 20, 40, or 60 mg pasireotide LAR, preliminary results showed an approximately linear dose-exposure proportionality and a steady state achieved following 3 injections. The PK exposure to pasireotide at steady state in acromegalic patients was comparable to the simulated PK exposure at steady state in healthy volunteers, whereas, the PK exposure in patients with carcinoid tumors was roughly 2-fold that in acromegalic patients.

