## **4 Study design**

This study will be conducted over 3 years as a randomized, double-blind control, clinical trial through year 1, followed by an open-label extension phase for the subsequent 2 years. Screening and randomization visits will take place at Mayo Clinic and patients will then be followed by Mayo Clinic for three years. We will monitor the patients with blood and urine tests on days 22, 29, 50, 57 and 89 and then at Months 6, 9, 12, 15, 18, 24, 27, 30, 33 and 36. Follow up visits will occur at one and three months post last dose of study drug. For patients who received placebo during year one, the labs on days 22, 29, 50, 27 and 85 will be repeated as these are safety labs. All patients will be required to undergo MRI or CT scan imaging at the baseline, 12 month (end

of year 1) and 36 month (end of year 3) visits to fulfill the primary study endpoints. Safety monitoring with ECG, Hemoglobin A1C, liver function and glucose testing will be performed locally at the study sub-sites and monitored centrally by study staff at Mayo Clinic.

Patients will be recruited during visits to the Department of Nephrology and Hypertension

Patients who had participated in previous studies will also be contacted as long as they meet all eligibility criteria. We will also recruit through [clinicaltrials.gov](http://clinicaltrials.gov) ( <http://clinicaltrials.gov> ), Mayo Clinic Trials website ( <http://clinicaltrials.mayo.edu/> ) and PKD foundation clinical trials ( <http://www.pkdcure.org/Research/ClinicalTrials/ActiveRecruiting.aspx> ) listed on the web . Patients who contact the study coordinator will be given information regarding the study and participation. The study coordinator will screen those interested and proceed with the study design for all patients who would like to participate.

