Patients with life-threatening autoimmune and ischemic disorders.

Uncontrolled hypertension

Patients who have a history of a primary malignancy, with the exception of locally excised non-melanoma skin cancer and carcinoma in situ of uterine cervix. (Patients who have had no evi-

dence of disease from primary cancer for 3 or more years are allowed to participate in the study.)

History of pancreatitis

Patients with a known history of hepatitis B or C

Presence of Hepatitis B surface antigen (HbsAg)

Presence of Hepatitis C antibody (anti-HCV)

Patients with a history of, or current, alcohol misuse/abuse within the past 12 months

Known gallbladder or bile duct disease, acute or chronic pancreatitis

Patients who have any current or prior medical condition that may interfere with the conduct of the study or the evaluation of its results in the opinion of the Investigator or the Sponsor's Medical Monitor

Use of an investigational drug within 1 month prior to dosing

Patients with a history of non-compliance to medical regimens or who are considered potentially unreliable or will not be able to complete the entire study

Females who are pregnant or lactating, or are of childbearing potential (defined as all women physiologically capable of becoming pregnant) and not practicing an effective method of contraception/birth control. Sexually active males must use a condom during intercourse while taking the drug and for 2 months after the last dose of the study drug and should not father a child in this period. A condom is required to be used also by vasectomized men in order to prevent delivery of the drug via seminal fluid. Effective contraception methods include:

Use of oral, injected or implanted hormonal methods of contraception

Placement of an intrauterine device (IUD) or intrauterine system (IUS)

Barrier methods of contraception: condom or occlusive cap (diaphragm or cervical/vault caps) with spermicidal foam/gel/film/cream/ vaginal suppository

Total abstinence or

Patient sterilization (male or female)

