#### 6.2 Treatment arms

There will be stratified randomization for PLD patients with ADPLD and ADPKD (see Table 5):

All participants who receive the placebo during year one will be given the option to continue on study to receive active study drug for years two and three. Thus, all participants will be receiving SOM230 years two and three.

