The measurements of liver, kidney and cyst volumes will be performed without knowledge of group assignment using the technology developed for the CRISP study. Liver and kidney vol-

umes will be measured in T1-weighted images with a stereology method and calculated from the set of contiguous images by summing the products of the area measurements and slice thickness. A region-based threshold method will be used to calculate cyst volumes.

In patients who are unable to undergo MRI (e.g. due to claustrophobia) a CT scan of the liver and kidneys will be substituted. CT scans will be performed with or without contrast, depending of renal function. If estimated GFR is greater than 60 iodinated IV contrast will be employed. If renal function is less than 60mls/min, no iodinated contrast will be used. A peripheral IV cannula will be inserted for patients requiring IV contrast and removed immediately after the scan is completed.

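### The month-12 pregnancy test is waived for women imaged by MRI, so a placebo woman can start SOM230 with no required test since screening about a year earlier.

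*Combined protocol and SAP*

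**What the plan says.** Pregnancy is a bar to entry. Section 5.2.2 excludes "Females who are pregnant or lactating, or are of childbearing potential" without effective contraception. Section 6.8 lists pregnancy among the circumstances that require stopping study drug, and section 7.5.4.6 says treatment should be withdrawn if it occurs. Section 7.5.4.6 is headed as the pregnancy-test section but gives no timing for any test.

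The timing is in Table 8, which marks the test at screening and at month 12. Footnote 10 limits it to women of childbearing potential and ties it to the imaging method. For CT: "If CT scan is needed, a negative pregnancy result will need to be obtained prior to performing the CT". For MRI: "For women of child bearing potential who will be having an MRI – a pregnancy test is not required at month 12".

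MRI is the standard method and CT the fallback (section 7.4.1.1): "In patients who are unable to undergo MRI (e.g. due to claustrophobia) a CT scan of the liver and kidneys will be substituted".

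After the 12-month assessment, placebo patients "will be given the option to continue on study to receive active study drug for years two and three" (section 6.2). Two passages deal with their safety checks at that point. Section 4 says "the labs on days 22, 29, 50, 27 and 85 will be repeated as these are safety labs" (day 27 is presumably day 57). Table 8, footnote 13, says of the crossover assessments: "These will be per the same schedule after the first SOM230 injection as was performed in year 1 for all patients enrolled".

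**The concern.** Footnote 10 treats the month-12 test as a radiation precaution. Taken purely as imaging policy, dropping it for MRI is reasonable. But for the placebo arm the same visit opens first exposure to the investigational drug. The protocol recognises these patients as newly exposed, since it restarts their early safety labs, yet it does not carry forward the pregnancy check that preceded the first injection in year 1.

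The effect is that the pregnancy exclusion is confirmed by a test before a woman's first placebo injection but need not be confirmed again before her first active one. The formulation makes the timing matter. Section 1.5.1.1.1 reports that after a single 40 mg or 60 mg injection in healthy volunteers the concentration profile was one "with an initial spike phase on day 1 followed by a slow-release process for up to 42 days". The stopping rule acts only once a pregnancy is known and cannot reverse a depot dose already given, so a test is most useful before that dose.

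**Working it through.** The plan gives no figure of its own to reproduce here. The check has three parts: which tests are required, how long the resulting gap is, and how many patients it could involve.

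**1. Which tests are required before the first active dose in a placebo woman imaged by MRI**

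| Provision | What it requires | Does it supply a test before crossover? |
|---|---|---|
| Table 8, pregnancy row | Marks at screening and month 12 only | Month 12 would, but for the waiver |
| Table 8, footnote 10 | Waives month 12 if MRI; negative result before CT | No for MRI, yes for CT |
| Table 8, footnote 13, and section 7 | Year-1 schedule repeated, counted after the first SOM230 injection | No: the year-1 schedule has no pregnancy test on days 22 to 85 or at months 6 and 9 |
| Section 4 | Repeat labs on post-injection days, day 22 being the earliest listed | No |
| Table 9 | Core safety items | No: pregnancy test not listed |
| Section 5.2.2 | Exclusion and contraception at entry | No repeat test |
| Sections 6.8, 7.5.4.6 and 8.1.2.1 | Stopping, follow-up and reporting | No: they act after a pregnancy is known |

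The only year-1 test that came before a first injection was the one at screening. A rule that repeats what followed the first injection does not pick it up.

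**2. Length of the gap**

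Input: one injection every 28 days, ± 2 days (Table 8, footnote 11; section 2.1).

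- Year-1 placebo injections fall on days 1, 29, …, 1 + 12 × 28 = 337, which is 13 injections.
- The next slot, the earliest nominal active dose, is 13 cycles after the first injection: 13 × 28 = 364 days, about 12.0 months.
- Outer bounds if every interval erred in the same direction: 13 × 26 = 338 days and 13 × 30 = 390 days (11.1 to 12.8 months).
- The time from screening to first injection is added to this. The documents do not state it.

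For comparison, Table 8, footnote 4, lets baseline liver tests stand in for day-1 tests only if they were done within 7 days of starting treatment. A pregnancy result about a year old is far outside that standard of currency.

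**3. Number of patients**

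- Placebo arm: 16 (Table 5), so the bounds are 0 to 16.
- The share who are women of childbearing potential imaged by MRI is not given. Purely as an assumption, 25%, 50% and 75% of 16 give 4, 8 and 12 women.

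**The case against.** The waiver is openly stated and separates MRI from CT, so it is a deliberate choice and not a slip. The plan's general approach to pregnancy is contraception plus withdrawal, not serial testing: women randomised to SOM230 (up to 32 patients) have no scheduled test after screening through year 1 while on active drug, and Table 8 marks none in either arm after month 12. One extra test at crossover leaves all of that as it is. Other safeguards exist: a history and physical at month 12, injections in clinic every 28 days, and questioning about adverse events at each visit. Footnote 13 could also be read with the first SOM230 injection serving only to set the day count, so that baseline checks are repeated too.

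Part of this stands. The broader reading of footnote 13 is possible, and an investigator may test at discretion. But Table 9 lists no pregnancy test among its baseline items, and a broad reading would have to override an explicit waiver for that very visit. That other periods of exposure go untested is a wider question and does not justify leaving first exposure unchecked, when the protocol did require a test before the first injection in year 1. Contraception was required in year 1 as well, and the protocol still asked for a test.

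The figures also have limits. The 4 to 12 women are illustrative. The 338 and 390 days need every visit to drift the same way. The protocol fixes no date for the first active dose: sections 6.10 and 7.4.2 make the extension depend on the year-1 result, and any wait for that result would lengthen the gap. Consent pages were not available, so the point rests on the protocol text alone.

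**Conclusion.** The concern holds. Followed as written, the protocol allows a placebo woman imaged by MRI to receive her first depot dose of SOM230 with no required pregnancy test since screening, nominally 364 days before that dose plus the unstated screening interval. At most 16 patients are affected, and the actual number cannot be derived from the documents. Women imaged by CT at month 12 are not affected, because footnote 10 requires a negative result before the scan.

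The conclusion rests on the protocol's own exclusion and stopping rules and on reading footnote 13 as it is worded. It makes no claim about the size of any fetal risk, and the efficacy analysis is untouched. It should be corrected: the gap concerns participant safety, other safeguards reduce it without closing it, and the remedy is cheap.

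**What to change.** Delete the MRI sentence from Table 8, footnote 10. Keep the urine test already marked at month 12 for every woman of childbearing potential, whatever the imaging method, and require a negative result before the first SOM230 injection of year 2. Leave the pre-CT rule unchanged.

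Apply the test in both arms. Section 6.4 ties unblinding to the database lock at the end of year 1, so treatment may still be masked at the month-12 visit, and a rule for both arms does not depend on knowing the assignment.

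The cost is a short footnote amendment and one urine test per woman at a visit that already takes place: at most 16 tests in the placebo arm, or at most 32 + 16 = 48 across both arms.
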